The patient ppt will meet with their assigned Coach for 8 weekly sessions. Sessions 2-8 are expected to last 30 min. These sessions will be audio recorded and uploaded to the study database alongside the patient ppt's responses to GAD-7 and PHQ-9 for ongoing supervision and monitoring by [name].

4. Subsequent assessments

See the Assessment Schedule for details of follow-up assessments.

Patient Participants: Patient participants will complete post-intervention assessments at Week 8, including brief exit interview questions of their experiences. They will also complete follow-up assessments to assess maintenance of treatment effects at 6 and 12 weeks after completion of treatment. These assessments can be conducted by Zoom, in-person at UNLV, or over the telephone. Patient participants will receive \$40 incentive payment for completion of each assessment (baseline, post-treatment, 6- and 12-week follow-up) for a total possible incentive of \$160.

Assessments and STARS sessions will be audio recorded for training and fidelity review.

BL, Wk 8, FU 1, FU2:

For all study-related assessment timepoints once enrolled, an RA will conduct the HAM-A clinical interview. The remaining instruments will be completed as self-report forms either using paper forms, for RA entry into the study database, or entered directly into the study database as survey responses by the participant.

For BL and Wk 8 assessments, this assessment visit will occur in person in the TREATment Lab space prior to their scheduled STARS coaching visit. After completion of the HAM-A interview, the participant will have time to complete the remaining self-report inventories.

For follow-up assessments (FU 1 and FU 2), the HAM-A will be conducted over the telephone and/or Zoom. The self-report forms will be completed either over the telephone (by verbal self-report from the patient participant) or possibly by emailing a survey link via REDCap. (Note: UNLV REDCap is still pending as of 7/11/2023 per [name], ORI Data Privacy Officer, so exact functions have not yet been trialed to see if we can build this function into our database.)

STARS Visits:

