Coach Participants: Coach participants will be paid \$10 per session completed with a patient participant (x 8 sessions = up to \$80 per patient). Coaches will receive \$50 for participation in the exit interview.Patient Participants: Patient participants will receive \$40 incentive payment for each completed assessment (baseline, post-treatment, follow-up 1, follow-up 2). These will be issued in the form of a Forte payment card and reloaded as indicated. Total for completion of all assessments: \$160. Attendance in STARS interventions are not incentivized.

No

*required

Indicate the method of payment.

✓ Forte System Gift Card

The Forte Research Payment System asks for participant identifiers (name, gender, email, mailing address, and date of birth). In the consent form, please include that participants may be asked to provide their name, gender, email, mailing address, and date of birth for compensation purposes. Specify if these identifiers will or will not be linked to their study data.

Research Credit/Extra Credit

Other

*required

When and how is the compensation provided to the subject?

Most studies require partial compensation be given for partial participation. Please address if payment will be prorated.

Coach Participants: Coaches will earn incentives per session completed (or, if the patient participant ends the session prematurely, the coach will still earn payment). Although recruitment and training will emphasize the desire for coaches to see approximately 3 patient participants each to learn and improve on their intervention delivery, there is no consequence if they do not see that many patient participant; payment will still be based per session. All coaches who enroll will be invited to complete the exit interview to ensure variety of viewpoints; for this, they are eligible to receive \$50 payment. Patient Participants: Study participation entails several assessments along the time course of study completion. Participating in assessments is incentivized; there is no monetary incentive for participating in the investigational psychotherapy. Participants may elect to discontinue treatment and still complete assessments, for which they will receive compensation.

Study Procedures

*required

Will the study involve administering and/or collecting data from any of the following?

Check all that apply.

Drugs

Devices (includes software and mobile applications)

Biologics

Medical Records

✓ None of the above

*required

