Patients with current suicidal ideation or a history of suicidal behavior will be ineligible to participate in this study. Individuals who develop active suicidal ideation will be removed from the study and referred to the crisis line, their PCP, and other relevant clinical services by the PI. Patients who develop passive suicidal ideation or who evidence \geq 30% increase in PHQ-9 or GAD-7 may be permitted to remain in the study and receive the intervention; they will also meet with the PI to discuss appropriate treatment recommendations (e.g., PCP, the UNLV PRACTICE, other resources). Investigators will follow up to ensure this connection takes place. This may include obtaining permission from the patient ppt for the PI to contact the PCP to discuss the clinical concerns and assist the PCP in management recommendations. Study research coordinators are trained to assess manic and psychotic symptoms and will conduct follow up assessments.

In non-emergent cases of active ideation (e.g., nonspecific thoughts of wanting to kill oneself), the patient participant will be allowed to continue with the day's planned coaching session and any scheduled assessments, as more information (e.g., from a clinical interview) may assist with better understanding and documenting the worsening. If the patient participant does not continue with a scheduled assessment because of PI discretion, they will still receive payment for their next scheduled assessment (either same-day or otherwise close in time; e.g., scheduled Week 8 assessment and PI withdraws patient participant after week 6 or 7 session).

b) Risk associated with intervention: The STARS program is a brief, structured behaviorally-based mental health intervention that is based on and informed principles from cognitive behavioral therapy (CBT), a well-known and extensively researched treatment paradigm for depression and

anxiety. The PI is a licensed clinical psychologist, clinical supervisor, and graduate faculty instructor with specialty in CBT and clinical trials conduct. To limit distress, research personnel and coaches will be trained and supervised by the PI in procedures for helping patients cope with protocol-generated concerns, stress, and anxiety.

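### Patients removed for active suicidal ideation are not clearly kept in the Week 8 and follow-up assessments, as patients who choose to stop treatment are

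*Protocol*

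**What the plan says.** The main text is in the Protocol, under the procedures to minimize risk, patient item (a), clinical deterioration and suicide risk.

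- On active ideation: "Individuals who develop active suicidal ideation will be removed from the study", with referral to crisis and clinical services.
- Patients with passive ideation, or a rise of 30% or more in PHQ-9 or GAD-7, "may be permitted to remain in the study and receive the intervention".
- In non-emergent cases of active ideation the patient is "allowed to continue with the day's planned coaching session and any scheduled assessments".
- On payment, for a patient who "does not continue with a scheduled assessment because of PI discretion, they will still receive payment for their next scheduled assessment". The example given is "scheduled Week 8 assessment and PI withdraws patient participant after week 6 or 7 session".
- On staff: "Study research coordinators are trained to assess manic and psychotic symptoms and will conduct follow up assessments".

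The Compensation section deals with patients who stop by choice: "Participants may elect to discontinue treatment and still complete assessments, for which they will receive compensation".

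Under Research Methods, item 4 (subsequent assessments), Zoom, in-person and telephone contact are all allowed in general. For baseline and Week 8, however, the text then says that "this assessment visit will occur in person in the TREATment Lab space prior to their scheduled STARS coaching visit". The two follow-ups are timed at 6 and 12 weeks after treatment is completed.

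The SAP analyses HAM-A and MEAQ, the primary clinical outcomes, with paired t-tests. It evaluates clinically meaningful change in the primary outcome by the Reliable Change Index (RCI), movement out of the clinical range and percent reduction. It states no rule for missing scores.

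**The concern.** The paired t-test and the RCI need a baseline and a post-treatment score from the same patient. HAM-A and MEAQ are described only at baseline, Week 8 and the follow-ups, so a patient removed mid-treatment who is not seen again has no post score. The Week 8 exit questions are lost as well.

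That loss would not be haphazard. The patient leaves because the clinical state worsened, while a patient who stops by choice can still be assessed. With 15 to 25 patients and no missing-data rule, the improvement rates would be computed without the very patients whose coaching was stopped for safety. The Protocol says that it tracks deterioration partly to document the intervention's safety, so those patients' outcome scores are worth having.

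**Working it through.** **1. The texts side by side.**

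| Patient | Coaching | Week 8 and follow-ups |
|---|---|---|
| Stops by choice | Ends | Kept expressly, and paid |
| Passive ideation, or score rise of 30% or more | May continue | May remain in the study |
| Active ideation, non-emergent | That day's session allowed | Scheduled assessments allowed; Week 8 and follow-ups not named in that clause |
| Active ideation, emergent | Ends | Removal from the study; no visible provision |
| Withdrawn by the PI after session 6 or 7 | Ends | Next assessment paid; collection not required |

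The sentence on passive ideation names the study and the intervention separately. Removal from the study is therefore not naturally read as only the end of coaching. The sentence on coordinators does not say whom they assess.

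**2. What is kept in any case.** The ideation itself meets the Protocol's definition of clinical deterioration. The patient counts as a non-completer in the SAP's retention measure. GAD-7 and PHQ-9 exist up to the last session attended. The loss is confined to the Week 8 and follow-up measures. The visible text does not say when AIM, FIM and IAM are given, so whether they would be lost is unknown.

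**3. How likely is any removal?** The Protocol's planned numbers reproduce: 5 coaches × 3 = 15 patients at minimum, 5 × 5 = 25 at most. It gives no rate of active ideation, so the per-patient risk p is an assumption, taken as independent between patients.

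- P(no removal) = (1 − p)^n. For n = 15: 0.860 at p = 1% and 0.739 at p = 2%. For n = 25: 0.778 and 0.603.
- At least one removal is more likely than not only if p exceeds 1 − 0.5^(1/n): 4.5% for n = 15 and 2.7% for n = 25.

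**4. Effect on an improvement rate.** Let m of n enrolled patients have no post score and count as not improved, and let r patients improve. The assessed-only rate is r/(n − m) and the all-enrolled rate is r/n. The relative excess is n/(n − m) − 1 = m/(n − m).

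| m | n = 15 | n = 25 |
|---|---|---|
| 0 | 0 | 0 |
| 1 | 1/14 = 7.1% | 1/24 = 4.2% |
| 2 | 2/13 = 15.4% | 2/23 = 8.7% |

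For illustration, 7 of 14 assessed (50%) is 7 of 15 enrolled (47%), and 12 of 24 (50%) is 12 of 25 (48%).

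**5. Effect on mean change.** Not sized. The answer would be set by whatever scores one assumed for the removed patients, and the documents give no basis for such values.

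**The case against.** The strongest reply is that the Protocol already handles most of this. The non-emergent clause is justified by the value of further information, such as a clinical interview, for documenting the worsening. The only patient clinical interview named among the research assessments is the HAM-A, which is given at baseline, Week 8 and the follow-ups. The payment rule is conditional on PI discretion and covers assessments that are not on the same day. Read together, these suggest that assessment continues by default with a PI exception. Research Methods also allows telephone or Zoom in general, and the in-person Week 8 wording applies equally to patients who stop by choice. The Risk of Harm Protocol, Assessment Schedule, consent form and attached study protocol were not seen and may settle the matter.

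Much of this stands. A reader might infer that the plan forbids or omits every assessment after active ideation; the documents do not support that. What remains is that the clause only allows, does not reach emergent cases and does not name the follow-ups, and that it sits beside a flat statement of removal. Two staff members could treat the same patient differently.

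The effect is also small. In the illustration, one removal moves 50% to 47% or 48%, while the standard error of a 50% rate is √(0.25/14) = 13 points or √(0.25/24) = 10 points. Current ideation and past attempts are exclusions, the Protocol calls later endorsement of PHQ-9 item 9 unlikely, and the trial is not powered for treatment effects. That supports a low grade. It is not a reason to leave an inexpensive ambiguity in place.

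Finally, research contact with an actively suicidal patient is a clinical judgment. That is right, and the fix leaves it with the PI.

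**Conclusion.** The point holds as a cheap improvement, with medium confidence. On the visible text, patients removed for active ideation could lack post-treatment HAM-A and MEAQ scores for a reason tied to their clinical state. The gap is clearest for emergent cases, patients withdrawn by the PI, and the two follow-ups.

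The number affected is unknown and may be zero. If there is one, the relative difference in the improvement rate is 4% to 7% across the planned sample sizes. This assumes that the patient is not assessed and counts as not improved.

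Three stronger inferences are not supported:

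- That the reported mean improvement is biased. The documents give nothing from which to estimate a shift.
- That harms go unrecorded. The deterioration definition, the retention measure and the session scores capture them.
- That paying for an assessment the PI stops is a fault. It is a fair protection for the patient.

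**What to change.** **Protocol, patient item (a).** Replace removal from the study with the end of coaching. Keep the referral, the PI's discretion and the payment rule. Add that Week 8 and both follow-ups are still offered, by telephone or Zoom if needed and without a coaching visit, when the PI judges it safe and the patient agrees. If an attachment already says this, a cross-reference is enough.

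**SAP.** Report RCI improvement and movement out of the clinical range twice: among patients assessed, and among all enrolled with those lacking a post score counted as not improved.

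**Optional.** Time the follow-ups for these patients from the planned Week 8 date, and list each safety removal with first and last session GAD-7 and PHQ-9.

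**Cost.** A few sentences in the Protocol, two or three lines in the SAP, and a minor IRB amendment, possibly with a consent-form change. Per removed patient: up to three extra contacts of up to 1 hour each, and at most 3 × $40 = $120, within the planned 4 × $40 = $160. If the existing rule already pays the next assessment, the addition is $120 − $40 = $80. Reported improvement rates may be slightly lower. Where the PI judges an assessment unsafe, the score stays missing.

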Strategies for Treating Anxiety Research Study

Contact PI: [name], University of Nevada, Las Vegas

Statistical Analysis Plan

This single-arm study will examine the preliminary feasibility, acceptability, and clinical outcomes among coach and patient participants. Statistical analyses will be conducted with IBM SPSS version 28. Means and standard deviations (SDs) for primary implementation outcome measures will be calculated as summary statistics for: Acceptability of Intervention Measure (AIM); Feasibility of Intervention Measure (FIM); and Implementation Appropriateness Measure (IAM). Feasibility and acceptability outcomes also include examination and summary of the following: (1) recruitment and retention of patient participants (number completing all study treatment visits as a proportion of those enrolled); (2) external rating of coach fidelity to intervention (proportion of those rated as "satisfactory" or above on fidelity rubric); (3) and summary statistics of patient-rated working alliance (Working Alliance Inventory-short form).

Differences between pre- and post-treatment scores on clinical outcomes will be examined using paired t-tests. Effect sizes will be assessed using Hedge's g, with 0.2, 0.5, and 0.8 representing small, medium and large effect sizes, respectively. Clinically meaningful changes in the primary outcome will be evaluated with: the Reliable Change Index (Jacobson & Truax, 1992), movement out of the clinical range, and the percent reduction in symptoms. RCI scores reflect the change in scores from baseline to posttreatment, divided by the standard error; therefore, it is a method of roughly estimating how far from zero the change in scores is per participant. RCI scores indicative of clinically significant improvement were greater than or equal to 1.96, or a decrease in score of roughly two standard errors (Jacobson & Truax, 1991).

Primary clinical outcomes include pre- and post-treatment changes anxiety severity (Hamilton Anxiety Rating Scale; HAM-A) and avoidance (Multidimensional Experiential Avoidance Questionnaire; MEAQ). Sustained change in anxiety symptoms on the HAM-A and MEAQ (pre-treatment and follow-up at 12 weeks) will also be examined with paired sample t-tests. Secondary clinical outcome is change between pre- and post-treatment global health status and functioning (World Health Organization's Disability Assessment Schedule 2.0; WHODAS 2.0) as assessed by paired sample t-tests. Additional exploratory analyses will examine pre- to post-treatment change and RCI scores in depressive symptoms (Patient Health Questionnaire; PHQ-9), given the high level of comorbidity between anxiety and depressive symptoms.

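### The pre-post change is estimated only by two-visit paired t-tests, so enrolled patients not assessed at Week 8 add nothing to the primary change, and the SAP has no plan for selective loss

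*SAP*

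**What the plan says.** **Analysis.** The second paragraph of the SAP states that "Differences between pre- and post-treatment scores on clinical outcomes will be examined using paired t-tests". The third paragraph names the targets: "Primary clinical outcomes include pre- and post-treatment changes anxiety severity (Hamilton Anxiety Rating Scale; HAM-A") and avoidance (MEAQ). Maintenance of change on these two scales ("pre-treatment and follow-up at 12 weeks) will also be examined with paired sample t-tests") has its own test. For WHODAS 2.0 the SAP gives one comparison: "Secondary clinical outcome is change between pre- and post-treatment global health status and functioning". It defines no analysis population, missing-data method or sensitivity analysis.

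**Data collection.** Under Research Methods, subsequent assessments, the protocol schedules Week 8 and then two later visits: "They will also complete follow-up assessments to assess maintenance of treatment effects at 6 and 12 weeks after completion of treatment". It adds that "For all study-related assessment timepoints once enrolled, an RA will conduct the HAM-A clinical interview" and that the remaining instruments are completed as self-report forms. The Compensation section keeps early stoppers under assessment: "Participants may elect to discontinue treatment and still complete assessments, for which they will receive compensation".

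**Circumstances of the Week 8 visit.** For baseline and Week 8, "this assessment visit will occur in person in the TREATment Lab space prior to their scheduled STARS coaching visit". The follow-up interviews are by telephone or Zoom. A sentence earlier in the same section allows any of the three modes for all post-baseline assessments, so the protocol does not say one thing on this. The risk-minimisation section removes patients who develop active suicidal ideation. Its payment example is a patient withdrawn after the week 6 or 7 session with Week 8 still to come.

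**The concern.** A paired t-test works on within-patient differences, so a patient with one of the two scores missing is not in it. Someone who misses Week 8 but answers the 6- or 12-week call adds nothing to the primary change. The baseline-to-Week 8 and baseline-to-12-week tests can then describe different patients, and setting them side by side as response and maintenance may mislead.

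The loss may well be related to outcome. Some patients who worsen are removed, and the Week 8 visit is tied to a coaching session that an early stopper no longer attends. The protocol's Objectives section offers the pre-post differences as early evidence for a later randomised trial. A biased mean change or Hedges' g would therefore be carried into the planning of that trial, and with 15 to 25 patients a few selective losses are enough to move it.

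**Working it through.** **1. Inputs from the documents.** Recruitment and Training of Coaches gives 5 coaches with 3 patients each, 5 × 3 = 15, and up to 5 each, 5 × 5 = 25. Both stated patient numbers are reproduced. No dropout rate, SD, correlation or expected change is given, so everything below that uses one rests on an assumption.

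**2. Pairs left.** Pairs = N(1 − d), where d is the share without a Week 8 score.

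| d | N = 15 | N = 25 |
|---|---|---|
| 10% | 14 | 22 |
| 20% | 12 | 20 |
| 30% | 10 | 18 |
| 40% | 9 | 15 |

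**3. Size of the shift.** The complete-pair mean differs from the all-enrolled mean by d × (mean change in those assessed − mean change in those missing).

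| d | gap 0.25 SD | gap 0.5 SD | gap 1.0 SD |
|---|---|---|---|
| 20% | 0.05 | 0.10 | 0.20 |
| 30% | 0.07 | 0.15 | 0.30 |
| 40% | 0.10 | 0.20 | 0.40 |

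At 30% missing, a shift of 0.1 to 0.3 SD corresponds to a gap of 0.1/0.3 = 0.33 to 0.3/0.3 = 1.0 SD. Against an assumed true change of 0.60 SD, that is 0.1/0.6 = 17% to 0.3/0.6 = 50%.

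**4. Paired analysis against a four-visit model, by mechanism.** Simulated normal scores, n = 15 and 25, about 30% missing at Week 8, true improvement 0.60 SD, correlations of about 0.5 with baseline and 0.7 among later visits. The model is maximum likelihood with an unstructured covariance. Bias is in SD units.

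| Week 8 missing depends on | Paired | Model |
|---|---|---|
| nothing (random) | about 0 | about 0, no meaningful loss of precision |
| baseline severity | 0.11–0.18, either direction | 0.04 or less, even if nobody returns |
| poor change to Week 8 | about 0.30, overstating | 0.13–0.24, overstating, smaller as more return |
| high Week 8 symptom level, half or more return | 0.15–0.19, overstating | about the same |
| high Week 8 symptom level, nobody returns | about 0.16, overstating | about 0.25, overstating |

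In the third row, with half of the missing patients returning later, root mean square error falls from 0.39 to 0.29 (n = 25) and from 0.42 to 0.34 (n = 15). The strength of selection matters: with a logistic slope of 0.5, 1 or 4 on the Week 8 change, the paired bias is about 0.15, 0.25 or 0.46 SD.

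**5. A second mechanism.** n = 25, 400 runs, true improvement 0.80 SD, Week 8 more often missing when the later scores are poor. All entries are overstatements in SD.

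| d | Paired | Model, none return | Model, half return | Model, all return |
|---|---|---|---|---|
| 10% | 0.04–0.05 | 0.08 | 0.04 | 0.00 |
| 20% | 0.08 | 0.16 | 0.07 | 0.00 |
| 30% | 0.10–0.11 | 0.22 | 0.08 | 0.00 |

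The model removes the bias when the later scores that drive the missingness are observed. It helps little when half are observed, and it is worse than complete pairs when none are.

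**The case against.** The study is declared exploratory and unpowered, the pre-post differences are called preliminary, and a paired t-test is a legitimate choice for a pilot. That stands. This is a gap in estimation and reporting, not an error in a stated figure. It does not remove the point, because the estimate is meant to inform the next trial and the plan would not show how far it depends on who was assessed.

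The model is no cure. Where missingness depends on the unseen Week 8 score, its assumption fails, and in some settings it does worse than complete pairs. Patients removed from the study may have no later scores to draw on. An unstructured four-visit covariance has 4 × 5/2 = 10 parameters, to be estimated from 15 to 25 patients. All of this stands, and it is why a not-at-random analysis and a simpler fallback covariance belong in the fix.

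A reader might infer more than the documents support:

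- *That only treatment completers are analysed.* A patient who stops treatment but attends Week 8 stays in the test. Those lost are the patients not assessed at Week 8.
- *That the follow-up scores are ignored.* The 12-week HAM-A and MEAQ scores have their own paired test, which would include an early stopper seen at 12 weeks.
- *That the SAP orders such patients excluded.* It is silent. The exclusion follows from the method.
- *That WHODAS is collected at follow-up and left unanalysed.* This is likely from the wording on the remaining instruments, but the protocol refers to an attached assessment schedule that is not among the documents. The same caution applies to MEAQ at 6 weeks.

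**Conclusion.** The point holds in this form. As written, the primary changes in HAM-A and MEAQ, and the secondary change in WHODAS, rest on patients with both a baseline and a Week 8 score. Nothing in the SAP measures or limits the effect of selective loss. At an assumed 30% missing, the paired analysis is off by roughly 0.1 to 0.3 SD. It overstates improvement if patients doing poorly are the ones missed, and it can err either way if loss follows baseline severity. Weaker or stronger selection widens the range. No single figure can be derived from the documents, because they give neither an attrition rate nor a mechanism. If loss is random or negligible, there is no bias. The change is worth making but not critical, and confidence is medium, because the gain from the model depends on the mechanism and on how many patients return.

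**What to change.** In the second and third paragraphs of the SAP:

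1. Define the analysis population as all enrolled patients.
2. Make the main analysis of HAM-A and MEAQ a likelihood-based repeated-measures model with all scheduled scores (baseline included) as outcome and visit as a categorical effect. Specify an unstructured within-patient covariance, a pre-stated simpler fallback such as compound symmetry, and small-sample degrees of freedom. Treat WHODAS in the same way if the assessment schedule confirms that it is collected at follow-up.
3. Report the baseline-to-Week 8 and baseline-to-12-week changes from that one model.
4. Keep the paired t-tests as a complete-pair sensitivity analysis, with the number of pairs in each and the baseline scores of the patients missing from it.
5. Add a simple not-at-random sensitivity analysis, for example assuming no change in patients with missing scores.

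The cost is SAP wording and a little more work in the software already named, with no extra visit or patient. The downside is that the model assumes missingness depends on observed scores. It can do worse than complete pairs if missingness follows the Week 8 symptom level and nobody returns, so items 4 and 5 should be reported beside it.
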